## 1.3 SCHEDULE OF ACTIVITIES (SOA)

Procedures	Screening & Enrollment Virtual Visit	Confirmatory Phone Call	Phone visit #1	Phone visit #2	Phone visit #3
Time Window (days)	-21	0	30 $\pm$ 7	60 $\pm$ 7	90 $\pm$ 21
Informed consent	X				
Demographics	X				
Medical history	X				
Confirmation of Device Set-Up		X			
COPD Assessment Test	X		X	X	X
COPD Exacerbation History	X		X	X	X
Inhaler Use and Compliance	X		X	X	X
Adverse Event Assessment		X	X	X	X
Complete Case Report Forms (CRFs)	X	X	X	X	X

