**4 STUDY DESIGN****4.1 OVERALL DESIGN**

This is a multisite, observational, 3-month pilot study of ProAir Digihaler use in 60 COPD patients at-risk for AECOPD. Participants will be recruited from two sites (Wake Forest University, N=30; University of North Carolina at Chapel Hill, N=30). All participants will have spirometry-confirmed COPD with an increased AECOPD risk (defined as two moderate or one severe AECOPD in the last 12 months).

Participants will be recruited from existing clinical pools at both sites including COPD registries, virtual and in-person outpatient clinics (routine or post-hospital discharge). Although this study will not be powered to make meaningful assessments of inhaler metric changes at the time of an AECOPD, we are permitting patients recently discharged for an AECOPD event to be enrolled, which will permit assessment of changes during the recovery phase as well as enrich for individuals more likely to have an AECOPD event during study.

In light of the COVID pandemic, this study is designed to be conducted entirely virtually to minimize any potential interruptions related to COVID. Both UNC and Wake Forest have experience conducting virtual studies with local IRB approval. Potentially eligible patients will be identified and screened for possible inclusion through existing registry review, virtual clinic visits or in-person visits.

Potentially eligible participants will be contacted, with the permission of their care providers, by study investigators or research coordinators and assessed for interest. Based on local IRB approval, they will either be mailed an informed consent (ICF) for phone review with the research coordinator or will complete verbal consent over the phone. After consenting, participants will be mailed the ProAir Digihaler (provided by Teva) The study coordinator will contact the participant to ensure set-up and correct usage.

Participants will then be asked to use the ProAir Digihaler as their primary mode of SABA therapy as they would in usual treatment and indicated in the product package insert and Instructions for Use. They will be provided a COPD Action Plan to ensure they have appropriate instructions to handle a possible AECOPD. They will answer a daily self-assessment asking "How are you feeling?" with responses provided on a Leikert scale on the DAQ App, as well as Digihaler metric algorithm-triggered DAQ on the DAQ app.

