#### **Specific Data Collection Includes:**

Clinical Data: Enrollment characteristics including age, race, sex, smoking history, prior spirometric data (FEV1, FEV1% predicted, FVC, FVC % predicted, FEV1/FVC), exacerbation history, enrollment inhaler regimen, self-reported frequency of albuterol use, baseline CAT score

Data Collection Tools: Enrollment questionnaire, CAT questionnaire, monthly AECOPD and self-reported albuterol use questionnaire, and Digihaler device. The Digihaler uses integrated sensors to capture inhalation data and stores it onto an e-module inside the device. When within range, the e-module transfers the stored data using Bluetooth technology to a paired app on the users' phone. The app can display the data in various reports as well as export the reports in the form of pdfs which can be emailed. The app also shares the data to a server via a wifi connection which enables real-time data sharing to a provider facing dashboard. The data the provider sees is the same as what patients see and also have the ability to be exported into a .csv file for further analysis. For additional data points, beyond what the patient and provider currently see, our team has the ability to export more information in the form of data extracts from the back end cloud server. This can be setup to send at a predetermined interval for further analysis.

**Patient Reported Outcomes (PROs):** CAT questionnaire, self-reported monthly average albuterol use during study, daily self-assessment asking “How are you feeling?” with responses provided on a Likert scale on the DAQ app, and Dihaler metric algorithm-triggered symptom questions using the DAQ app.

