### 8.1 OUTCOME ASSESSMENTS

- Digihaler PIF: mean, median, standard deviation
- Digihaler Inspiratory volume: mean, median, standard deviation
- Digihaler Inhaler usage: count
- Self-reported inhaler usage: Average use over the preceding month
- COPD Assessment Test (CAT) questionnaire: Collected monthly
- Self-report of COPD exacerbation events on study
- Responses to daily self-assessment asking "How are you feeling?" on Leikert scale (mean, median, standard deviation, variability)
- Responses to DAQ on the DAQ app (cumulative score and individual domains mean, median, and standard deviation; variability of the responses and adherence to daily reporting)

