### 9.3 MISSING DATA

The primary analyses will be “per protocol” analyses. Adult subjects must complete baseline and one month phone visit at minimum to be included in analysis. Subjects who complete these required visits will be included for analysis, and subjects who do not complete required visits will be excluded from the statistical analyses. Safety analyses will be included for all subjects. Reasons for drop-out and missing data values will be documented in the database. The occurrences of drop-out and missing data will be examined to investigate potential induction of selection biases. Missing data (i.e., occurring during hospitalization) will be assumed to be missing not at random. These missing data will not be imputed.

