### 9.4 STATISTICAL ANALYSES

Below are the pre-specific outcome measures:

Primary Outcome Measure:

1. Variability in Peak Inspiratory Flow (PIF) Measured via Digihaler Device (Time Frame: Three months)
  - b. PIF is the maximal flow occurring during an inhalation effort, expressed in Liters/minute. Mean, standard deviation and coefficient of variation (calculated by dividing standard deviation of PIF by the mean of the PIF) of daily PIF measurement collected over three months will be calculated. PIF will be measured using the Digihaler device.

Secondary Outcome Measures:

1. Correlation of Self-Reported Inhaler Use with Actual Inhaler Use (Time Frame: 3 months)

- a. Correlation between self-reported inhaler use and actual inhaler use over three months will be calculated with Spearman rank-order correlation coefficient. Self-reported inhaler use will be determined with an investigator-developed single question categorizing average use over the last four weeks with five groups (not at all, once a week or less, two or three times a week, one or two times a day, three or more times a day). Actual inhaler use will be directly measured via Digihaler device and categorized into one of the five groups described above.
2. Variability in Inhalation Volume Measured via Digihaler (Time Frame: Three months)
  - a. Inhalation volume is the volume of air inspired during an inhalation effort, expressed in Liters. The mean, standard deviation and coefficient of variation (calculated by dividing standard deviation of inhalation volume by the mean of the inhalation volume) of daily inhalation volume measurements collected daily over three months will be calculated. Inhalation volume will be measured using the Digihaler device.

The primary analysis will be descriptive, with analytical plans as defined above for each primary and secondary outcome.

The primary analysis will be descriptive, with analytical plans as defined above for each primary and secondary outcome.

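### Secondary outcome 1 sorts a measured device rate into five answer options that leave gaps, with no stated counting unit and no rule for turning monthly answers into one three-month coefficient

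*Combined protocol and SAP*

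**What the plan says.** Section 9.4 (repeated in the synopsis, 1.1) defines secondary outcome 1 as one coefficient: the correlation of self-reported and "actual inhaler use over three months will be calculated with Spearman rank-order correlation coefficient". Self-report is a single question on average use over the last four weeks with five options: none, up to once a week, then "two or three times a week, one or two times a day", and three or more a day. For the device side: "Actual inhaler use will be directly measured via Digihaler device and categorized into one of the five groups described above". Neither place gives cut-points, a rounding rule, a counting unit or an averaging window.

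Other sections bear on the same outcome:

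- Section 8.1 lists "Digihaler Inhaler usage: count", and section 3 names the device metric as the number of inhalation events. Section 6.1.2 describes an administration as 2 inhalations. The eligibility rule in 5.1 counts regular use in puffs.
- The schedule (1.3) marks "Inhaler Use and Compliance" at screening and at all three phone visits. Section 6.1.1 lists "self-reported frequency of albuterol use, baseline CAT score" among the enrolment data and, separately, self-reported monthly average use during the study among the patient-reported outcomes.
- Section 4.1: "After consenting, participants will be mailed the ProAir Digihaler". The screening answer therefore predates the device.
- Section 9.3: "Adult subjects must complete baseline and one month phone visit at minimum to be included in analysis". Some analysed patients may have only one on-study answer.

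**The concern.** A respondent facing five options can choose the nearest one. A measured average cannot, so the device side needs explicit boundaries, and the stated rule cannot be carried out for every patient without inventing them.

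Two further choices are open. If patients answer in occasions and the analyst groups raw inhalations, the device group can move upward with no change in behaviour. And the coefficient is for three months while each answer covers four weeks, so an analyst must decide whether to average, pool or select answers and which device days to match. Two analysts could report different coefficients from the same data, and these choices could be made after the data are seen. This is the first-listed secondary outcome, and accurate assessment of rescue use is part of the study's rationale (2.1, 2.2).

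**Working it through.** The plan states no expected correlation, power or precision, so there is no figure of its own to reproduce.

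**Step 1: gaps.** Convert each option to a weekly rate and multiply by 4 for a 28-day total.

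| Option | Per week | 28-day total |
|---|---|---|
| None | 0 | 0 |
| Up to once a week | >0 to 1 | 1-4 |
| Two or three a week | 2 to 3 | 8-12 |
| One or two a day | 7 to 14 | 28-56 |
| Three or more a day | 21 or more | 84 or more |

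The totals without a group are 5-7 (3 values), 13-27 (15) and 57-83 (27): 3 + 15 + 27 = 45 of the 85 totals from 0 to 84. This counts values, not patients; every total above 84 has a group.

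**Step 2: unit.** Two uses a day at 2 inhalations each is 2 × 2 = 4 events a day. That is the fourth group counted as uses and the fifth counted as inhalations. Three uses a week is the third group as uses; as inhalations it is 6 a week, which has no group.

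**Step 3: size, under assumptions.** The documents give no use distribution, recall error or capture rate. Assume a lognormal use rate (median 3, 7 or 14 occasions a week, log-SD 0.7 or 1), Poisson occasions over 28 days, self-report equal to realised occasions times lognormal noise (log-SD 0.5, no systematic under-reporting), and all use on the device. With 100,000 simulated patients per scenario, the ranges over scenarios and over ways of closing the gaps are:

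| | 1 inhalation per occasion | 2 per occasion |
|---|---|---|
| Device total in a gap | 33%-52% | 19%-45% |
| Grouped Spearman | 0.63-0.81 | 0.49-0.80 |
| Device group above self-report | 8%-18% | 32%-58% |

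- Within a scenario, going from 1 to 2 inhalations lowers the grouped coefficient by 0.00-0.14.
- At 1 inhalation per occasion, the gap rule alone moves it by 0.03-0.06 with the same cuts on both sides, and by at most 0.11 if only the device cuts vary.
- With midpoint cuts, the grouped coefficient falls as low as 0.56 at 2 per occasion. Spearman of self-report with the ungrouped count is 0.73-0.85 and identical at 1 and 2, because doubling every count leaves the ranks unchanged. If half the patients take 1 and half take 2, it is 0.04-0.08 lower.
- At 2 per occasion with only half the occasions on the device, 9%-20% of patients are above their self-report group and 12%-25% below, so use outside the device can reverse the shift.

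**Step 4: pairing.** A separate simulation (1,000 trials of 60, month-to-month variation, recall log-SD 0.6 with about 18% under-reporting) compared one call, pooled calls and the mean answer. On the same data, pairing alone moved the mean coefficient by about 0.09 to 0.15. Across unit, gap rule and pairing together it ran from 0.58 to 0.85 at a median of 14 uses a week.

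**Step 5: windows.** The latest call 2 is day 60 + 7 = 67. Sections 1.1 and 4.1 explain the 21 days at the end as additions (14 for an exacerbation plus a 7-day window), which puts the earliest call 3 at 90 − 7 = 83. Two 28-day look-backs then overlap by up to 28 − (83 − 67) = 12 days. Read literally, 90 ± 21 in section 1.3 allows day 69 and an overlap of 28 − 2 = 26 days. A call on day 23 looks back at most 28 − 23 = 5 days (18%) before day 0. That is an upper bound on days without the device, since day 0 is a set-up call made within a week of receipt.

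**Step 6: sampling error.** The sampling SD of one grouped coefficient at n = 60 is 0.05-0.10 in the step 3 simulations. An approximate 95% interval around 0.7 is 0.52 to 0.82 (Fisher z, Bonett-Wright variance).

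**The case against.** Grouping both sides on one scale is a legitimate choice, and a sensible analyst would round to the nearest option. The outcome is descriptive, in a pilot without power calculations, and most single shifts are within sampling error. All simulated figures rest on assumptions. That the ungrouped coefficient is usually larger does not make it better. All of this stands and limits the weight of the point. But rounding to the nearest option is not written down, and sampling error does not excuse an avoidable choice that can be made after seeing the data.

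Three stronger readings are tempting, and the documents do not support them.

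- *The screening answer enters the coefficient.* Section 6.1.1 ties the patient-reported outcome to use during the study, and 4.1 ties it to the monthly calls. The on-study answers are evidently meant; only their combination is open.
- *The plan will manufacture the under-reporting hypothesised in 9.1.* Section 9.4 plans only a correlation for this outcome, with no comparison of levels. The upward shift needs patients to answer in occasions and analysts to count inhalations. Neither is stated, eligibility counts puffs, and the questionnaire, which is not in the documents, may define the unit. Rescue use outside the device, which 4.1 and 6.3 allow, can offset the shift.
- *Recall windows overlap by 26 days.* That follows only from the literal ± 21 window; the explanation in 1.1 and 4.1 gives 12.

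**Conclusion.** The point holds and is worth fixing before analysis, with modest impact. That the grouping rule has gaps follows from the text alone. That it affects about 20% to 50% of patients depends on the assumed use distribution. The counting unit is unstated, and grouping raw inhalations could, but need not, shift the device group upward. The way up to three four-week answers and their device days become one three-month coefficient is also unstated; in the simulations this matters at least as much as the gap rule. Nothing here invalidates the outcome or affects the primary analysis.

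**What to change.** 1. Compute Spearman between self-report and the **ungrouped device rate**, declared as a change from the stated derivation, with the grouped version as supportive. The reason is that it needs no device cut-points and is unaffected if every occasion is 2 inhalations.
2. For the grouped version, fix contiguous cut-points in advance at the midpoints between adjacent options: (1 + 2)/2 = 1.5, (3 + 7)/2 = 5 and (14 + 21)/2 = 17.5 a week. The groups become 0; >0 to <1.5; 1.5 to <5; 5 to <17.5; 17.5 or more a week. Count occasions of use if the device extract carries time stamps; otherwise show results at 1 and at 2 inhalations per occasion.
3. Pair each on-study call's answer with the device rate over the preceding 28 days, truncated at the first device day. State that the screening answer is not used.
4. Name one summary per patient, for example the mean answer over available calls against the mean device rate over the same windows. Per-call coefficients can be supportive, but calls must not be treated as independent. Reconcile the final-call window in 1.3 with 1.1 and 4.1.

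The cost is some derivation work and a supportive analysis; no new data and no change to the question. The midpoints, and any interval used to define an occasion, are partly arbitrary. Averaging answers treats the options as equally spaced. The ungrouped coefficient is not comparable with a grouped one and remains lower if patients differ in inhalations per occasion. How patients at 4 to 6 uses a week chose between options cannot be recovered.

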The participants will be contacted once per month to collect CAT score and self-reported average albuterol use over the preceding month. They will also be asked about any AECOPD events requiring treatment with antibiotics or steroids in the prior month. If there is evidence during the calls of clinical deterioration by self report or an abrupt increase in CAT by > 4 units patients will be advised to contact their primary care or COPD provider.

Participants will be enrolled for three months duration. In the event the participant has an AECOPD within two weeks of end of study, they will be followed for 14 days after AECOPD resolution. Total participant duration is three months (+21 days to account for 14 days in event of AECOPD and seven day window at end of study). In the event their ProAir Digihaler does not last three months, they will be prescribed another device (provided by Teva). Hospital admission during the course of the study will not prohibit continued participation.

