Additional exploratory analysis will include linear regression (continuous) or negative binomial regression (count) of the clinical and demographic factors associated with inhaler from primary and secondary outcomes; descriptive statistics (mean, median, variance estimate and 95% confidence intervals) of number of inhalation events, correlation of inhaler metrics (PIF, inhalation volume, number of inhalation events) with CAT score, correlation of inhaler metrics (PIF, inhalation volume, number of inhalation events) with daily self-assessment asking “How are you feeling?” with responses provided on a Leikert scale, correlation of inhaler metrics (PIF, inhalation volume, number of inhalation events) with responses to metric algorithm-triggered DAQ; change in inhaler metrics (during the 7 days after and/or leading into hospitalized AECOPD or home treatment of a moderate AECOPD defined by a prescription for steroids and/or antibiotics); descriptive statistics (proportion, 95% CI) of COPD-associated hospitalizations and emergency room visits as well as SABA utilization; and patient satisfaction will be assessed with a post-study survey. The Leikert scale will be modeled using an ordinal scale with lower number signifying worse daily overall feeling. The DAQ will be comprised of yes/no responses to a set of questions (categorized as No=0; Yes=1) with higher score calculated in the analysis indicating worse symptoms. In exploratory analyses, individual DAQ domains and cumulative score will be evaluated as outcomes. Because the DAQ also includes the Leikert scale, on days where both the DAQ Leikert and daily Leikert are completed, the DAQ Leikert will be used for analysis.

---

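### Number of inhalation events is planned as a count with no time denominator or offset, although the plan's own rules give patients unequal observed time

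*Combined protocol and SAP*

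**What the plan says.** Section 3 names number of inhalation events, with PIF and inhalation volume, in the primary objective, and again in the secondary objectives on CAT domains and the daily self-assessment. Section 8.1 gives its form as "Digihaler Inhaler usage: count". Section 9.4 plans "descriptive statistics (mean, median, variance estimate and 95% confidence intervals) of number of inhalation events" and, for modelling, "linear regression (continuous) or negative binomial regression (count) of the clinical and demographic factors associated with inhaler". No time unit, offset or fixed window is attached to either. In the same section, PIF and inhalation volume are defined on daily measurements, and actual use is put on a per-week or per-day scale only for the five-group Spearman correlation with self-report.

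Three rules set how long a patient is observed:
- Section 9.3: "Adult subjects must complete baseline and one month phone visit at minimum to be included in analysis". Section 1.3 schedules that visit at 30 ± 7 days.
- Section 1.3 schedules the last call at 90 ± 21 days.
- Section 4.1 says of patients with an AECOPD in the last two weeks that "they will be followed for 14 days after AECOPD resolution". It splits the extra 21 days into 14 for such an event and 7 for the end-of-study window.

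Section 9.3 gives time in hospital as an example of missing data and adds: "These missing data will not be imputed".

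**The concern.** A count accumulates with time. If patients are observed for different lengths of time and the count is not divided by that time, a short stay looks like low use and a long stay like high use. Two features make this more than noise. Leaving early may be related to patient characteristics that enter the regression. Part of the extra time at the end is given because of an AECOPD, an event the study itself examines. In an undivided total, missing hospital days also add nothing, as if the inhaler had not been used.

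At stake are the between-patient spread of use, which the primary objective asks for, the average level of use, and the coefficients of the negative binomial model. Any factor linked to drop-out or to a late AECOPD would pick up a false association with use.

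**Working it through.** **Inputs from the documents**
- Earliest entry to the analysis: 30 − 7 = day 23 (Sections 1.3 and 9.3).
- Last call: 90 − 21 = day 69 to 90 + 21 = day 111 (Section 1.3).
- Longest participation, taking three months as 90 days: 90 + 14 + 7 = 111 days (Section 4.1). This reproduces the upper edge of the last-call window.
- Part tied to a late AECOPD: 90 + 14 = day 104.

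**Assumptions, not in the documents:** rate of use, its spread, and the proportion and timing of drop-out.

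**Step 1. One patient.** At a constant rate r, the expected count over d days is r × d. Relative to a 90-day completer it is d/90, whatever r is.
- Leaving at day 23: 23/90 = 0.26
- Leaving on days 30 to 60: 0.33 to 0.67, mean 45/90 = 0.50
- Followed to day 104 or 111: 1.16 or 1.23
- Completers at the two ends of the last-call window: 111/69 = 1.61-fold
- Full permitted range: 111/23 = 4.8-fold. At 4 inhalations a day this is 92 against 444 events.

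**Step 2. Overall mean, reading the count as a 90-day total.** Let a proportion p leave uniformly on days 30 to 60 and q run to day 111. The time factor is f = (1 − p − q) + 0.50p + 1.233q. With a true mean of 4 a day:
- p = 10%, q = 5%: f = 0.85 + 0.05 + 0.0617 = 0.9617, giving 3.85 a day (4% low)
- p = 20%, q = 10%: f = 0.70 + 0.10 + 0.1233 = 0.9233, giving 3.69 a day (8% low)
- p = 30%, q = 10%: f = 0.60 + 0.15 + 0.1233 = 0.8733, giving 3.49 a day (13% low)

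**Step 3. Between-patient spread.** Ignoring the small Poisson term, CV² of the count = (1 + CV² of the rate)(1 + CV² of time) − 1. The mean of (d/90)² is 7/27 = 0.259 for uniform days 30 to 60, and 1.521 at day 111. The assumed rate CV is 0.60, so 1 + CV² = 1.36.
- First mix: mean square 0.85 + 0.0259 + 0.0761 = 0.9520; CV² of time = (0.9520 − 0.9617²)/0.9617² = 0.029; count CV = √(1.36 × 1.029 − 1) = 0.63
- Second mix: mean square 0.9040; CV² of time 0.060; count CV 0.66
- Third mix: mean square 0.8299; CV² of time 0.088; count CV 0.69

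**Step 4. Regression.** In 1,000 simulated trials of 60, every group had the same true rate distribution (mean 2 a day, gamma shape 1). In each, 10-20% left on days 23 to 60 and 10-20% were followed to days 104 to 111. Omitting the log(days) offset multiplied the estimated rate ratio by 0.46 for drop-outs and 1.19 for late-AECOPD patients. These are the mean time ratios 41.5/90 and 107.5/90. The mean count divided by 90 was 1.82 to 1.93 a day; the mean per observed day was 1.99 to 2.00.

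**The case against.** The strongest reply is that the plan is silent and has not chosen a study total. In Section 8.1, count may only label the data type. Other analyses need a time unit: the five frequency groups, the correlation with a daily score, and the 7-day windows around an AECOPD. That stands: a reader might infer that the plan prescribes raw totals, and it does not say so. But none of those units carries over to the descriptive summary or the negative binomial model, so an analyst following the text has nothing that requires a rate.

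The model's target is also unclear. The sentence refers to primary and secondary outcomes, none of which is an inhalation total. This stands too, although number of inhalation events is the only one of the three inhaler metrics that is a count.

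Section 5.4 expects good retention, and Section 7.2 replaces withdrawn patients to reach 60 complete data sets. Replacement does not remove the problem, because Section 9.3 still keeps a leaver who completed the one-month visit. Section 9.3 does promise to examine drop-out for selection bias, but that examination does not correct the metric. Under Section 7.3, a patient counts as lost only when both calls and transmission stop, so some who miss calls will still supply data. That weakens the day-23 extreme.

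The listed outcomes have a three-month time frame, and whether extension days enter this count is unstated. If they do not, the late-AECOPD part falls away.

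The bias may also be small beside sampling error. With the inputs of Step 2, the standard error of the mean is 4 × 0.60/√60 = 0.31. The shift at 10% drop-out (0.15) is about half of that; at 30% (0.51) it is about 1.6 times. Finally, Section 9.2 describes a pilot without power calculations.

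**Conclusion.** The concern holds for number of inhalation events and SABA utilization. If the count is analysed as written, differences in follow-up add spurious variation between patients. Early drop-outs look like low users: about half a completer's count if they leave on days 30 to 60, about a quarter at the day-23 extreme. Late-AECOPD patients look like somewhat higher users, by about 16-23%. The effect on the mean depends on drop-out, which the documents do not give: about 4% low at 10% and 13% low at 30%, both assumed and both reading the count as a 90-day total.

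Three stronger readings are tempting and not supported:
- **The 4.8-fold range is typical.** It compares the earliest permitted visit with the latest permitted end, and assumes that device data stop at the call.
- **Late-AECOPD patients are seriously misclassified as heavy users.** The time effect is at most about 23%, and only 14 of the 21 extra days are tied to the event. Section 1.3 gives all patients the ± 21-day window. A true rise in use around the event would also remain in a per-day rate.
- **The primary outcome is compromised.** PIF variability is not a count and is unaffected, and Section 9.4 labels the count analyses exploratory.

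It is still worth changing, because the metric is in the primary objective and the better method is simple.

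**What to change.** In Sections 8.1 and 9.4:
- Define the metric as inhalations per observed day.
- Use log(observed days) as the offset in the negative binomial model, and name the model's outcome.
- Report SABA utilization the same way.
- Define observed days. Leave out hospital days, in line with Section 9.3, and count inhalations only over the days kept. Treat days after the last data transfer as missing. Judge this across all of a patient's devices, since each patient receives three inhalers (Section 1.1) and each device stores its own data (Section 6.1.1).
- Add a sensitivity analysis truncated at day 90.

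The cost is small: no new visits or patients. The analyst must derive observed days for each patient from device data and hospitalization reports. Section 6.1.1 describes back-end extracts but does not mention transfer dates, so confirm that they are held. If they are not, use enrolment and last-contact dates.
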